## 2 RATIONALE

In cardiac surgery, as in all branches of medicine, we treat patients so as to achieve two objectives:

[figure not shown]
- to improve quality of life (QoL)
- to improve survival

Deciding on an operation to improve survival is now easier due to sophisticated tools (EuroSCORE II & Tute) that measure and compare the risk to life of an operation with the risk to life from not having an operation. No such tool exists for QoL which is often the most important outcome for the patients.

Although some studies of cardiac surgery have included QoL as an outcome measure, no study has ever analysed the changes in QoL over time in the postoperative period and no study has ever analysed the relationship between individual patient and operation characteristics and the QoL outcome.

We know that most patients having heart surgery have symptoms (such as pain and breathlessness) which affect their QoL, and they submit to surgery in the hope of achieving relief from these symptoms and thus improving their QoL. We also know that, immediately after surgery, QoL is actually worse for all patients because postoperative pain, hospitalisation and functional limitation all have an impact. The normal scenario thereafter is that QoL then begins to improve, reaches the level it was before the operation and then hopefully exceeds it so that there will come a time when any QoL lost through surgery is 'paid back' by QoL gained. From that point onwards, the patient truly begins to benefit from having had the operation. The changes in QoL as a consequence of a typical major heart operation over time are graphically illustrated in the figure.

impact of a successful major open heart operation on quality of life

This is true for most patients, but not for all. A few will die from the operation. Some never regain the preoperative level of QoL, and some may not achieve a subsequent QoL improvement that matches or exceeds the QoL loss that occurs after the operation. Previous work indicates that between 8-19% of patients will experience a fall in QoL that does not recover.

When patients consent to major intervention, such as cardiac surgery, they need to know two things:

- 1) the risk to life of having an operation compared with the risk of not having an operation
- 2) the impact of an operation on QoL compared with the impact of not having an operation

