Currently, we are able to provide detailed individualised information on the first so that we can identify those patients likely to benefit in terms of survival. We do not have such individualised information for QoL. We know that, overall, there is a net benefit in QoL after heart surgery, but we also know that in a sizeable minority of patients, QoL may not improve and may actually worsen after heart surgery, yet we do not have the tools that allow us to identify the patients who will lose in QoL terms. This study will address this knowledge gap.

We shall use existing tools to measure QoL in patients having major heart surgery. QoL will be measured before the operation and monthly afterwards for 12 months in order to answer the following questions:

- 1) How does having heart surgery affect the QoL immediately after the operation?
- 2) How long does it take patients to return to the same QoL they had before the surgery, if they ever do?
- 3) How long does it take patients to regain any loss of QoL due to the operation? Does QoL improve thereafter? And to what extent?
  - a) In other words will surgery 'add value' to their QoL?
  - b) If so, when?
- 4) What proportion of patients will achieve a net benefit in QoL?
- 5) Are there features that can predict who will benefit in terms of QoL and who will not?

Based on the above findings we intend to create a risk model to predict the following:

- 1) who will experience QoL net improvement and who will not within 12 month of surgery.
- 2) what is the net gain/loss of QoL that an operation may produce, and for which patients?
- 3) how long before a patient having a heart operation begins to benefit in terms of QoL

We will use the data to develop an electronic calculator to enable quick and robust evaluation of the impact of heart surgery on the QoL of individual patients. The calculator will be tested by patients and their feedback will be used to refine it so that the final version made available in the clinical setting will function in an accessible, user-friendly and understandable way. Patients will then be in a position to decide if they wish to proceed to surgery based on a full knowledge of *both* surgical risk and the potential impact on QoL.

When completed, the study will:

- 1) improve the process of informed consent by patients
- 2) improve the process of medical decision making by doctors

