## 5. RECRUITMENT AND SAMPLING

### 5.1 Sampling

The study will recruit a total of 8004 patients over two years and follow them up for 12 months. This sample size was derived as follows: according to Abah et al the percentage of people expected not to regain QoL after heart surgery and after 12 months is between 8-19%. Additionally, there is a 4% predicted mortality rate for heart surgery in the UK in the higher risk population which is the subject of this study. Therefore, a conservative estimate is that 12% of patients in this study would not regain QoL. Assuming the 12% rate as a reference value, with a minimum of 6670 patients we would be powered to produce a predictor tool with a sensitivity of at least 0.75 (or true positive rate to identify those patients that do not regain QoL after surgery) and a 3% error ( $0.75 \pm 0.03$ ) at the 95% confidence level. Anticipating a non-response rate of 20%, we will recruit an additional 1334 patients to compensate for this, giving a total of 8004. Based on the above, the study will estimate the proportion of patients who do not regain QoL after 12 months with a 95% confidence of  $\pm 0.7\%$  (for a rate of 8%) and  $\pm 0.8\%$  (for a rate of 12%) with 6670 patients.

Recruitment and drop-out rates will be continuously monitored by the trial steering committee (TSC). To recruit 8004 patients, we plan to approach all 36 cardiac centres in the UK. Assuming only 30 centres take part (a feasible number based on our NIHR ETTAA study) and a two-year recruitment period, there will be 20000 patients with a EuroSCORE II  $\geq 3$  who would be eligible for the study over two years. Our sample size calculation requires that 40% of the eligible patients consent over the two-year period. This translates into no more than 134 patients per centre per year, a recruitment target that is conservatively achievable. Based on our original approach to 5 centres, the recruitment rate will average 192 patients per centre per year, so that the required 134 patients per centre per year is achievable and will be carefully monitored by the project management team and the TSC as described in the section 9.4 of this protocol.

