#### **5.5 Statistical analysis**

All statistical analyses and reporting will comply with CONSORT guidelines where possible.

Two single measures for QoL will be used for data analysis. The primary one is the mapping utility value of EQ-5D-5L; the other (as an alternative) is the SF-6D utility value mapped from SF12. An additional combine measure will be considered in case of considerable conflict in those two measures. This will be discussed formally in the statistical analysis plan.

Six outcomes will be used in all the analyses. The three primary outcomes will be defined as: (1) a continuous variable of a difference in the single measure of QoL between the baseline stage and a follow-up stage, this is a measure of the net QoL benefit ; (2) a binary variable of whether the post-surgery QoL has regained to the level at baseline; (3) a binary variable of whether the total sum of the first primary outcome over the follow-up time period where it is positive is larger to the period in which is negative, this is an indicator variable showing if a patient has achieved positive net QoL benefit. All the three primary outcomes will be based on EQ-5D-5L; the other three secondary outcomes derived from SF12 with the same definitions as (1), (2) and (3).

Three work packages will be designed to answer the aforementioned research questions of interest:

1. Perform descriptive statistics on (a) the first primary outcome at the stage immediately post-surgery; (b) the follow-up time (months) if the second primary outcome indicates the first occurrence of regaining (point estimate and confidence intervals); (c) the average trend of the first primary outcome over time; (d) the third primary outcome.
2. Perform inferential statistics on statistical testing to investigate the significance of variables in PANAS, LOT and patient frailty on the third primary outcome.

3. Develop a risk model on the third primary outcome by logistic regression or multilevel logistic regression.

In addition, the sensitivity analysis will be carried by doing the above three work packages replacing the primary outcomes with the three secondary outcomes based on SF12. The robustness of estimates and conclusions will be assessed. If a conflict exists, we may create a single measure of QoL by combining EQ-5D-5L and SF12 and do the same work packages.

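### As worded, time to regain baseline QoL is summarised only in patients who regain it, which understates recovery time for the whole cohort and does not answer research question 2

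*Protocol*

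**What the plan says.** Section 2 of the Protocol asks, as its second question: "How long does it take patients to return to the same QoL they had before the surgery, if they ever do". Section 5.5 defines the second primary outcome as "a binary variable of whether the post-surgery QoL has regained to the level at baseline". The definition carries no time point, no persistence rule and no minimum difference.

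Work package 1 in the same section is headed as descriptive statistics. Its item (b) is "the follow-up time (months) if the second primary outcome indicates the first occurrence of regaining (point estimate and confidence intervals"). No other listed analysis directly gives a time to return to baseline.

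The Protocol expects a substantial group with no such time. Section 2 says "Some never regain the preoperative level of QoL". Section 5.1 says "the percentage of people expected not to regain QoL after heart surgery and after 12 months is between 8-19"%, adds that "there is a 4% predicted mortality rate for heart surgery in the UK" in the higher-risk population studied, and concludes that "a conservative estimate is that 12% of patients in this study would not regain QoL". It also anticipates 20% non-response. Section 6.1 schedules QoL at discharge and then monthly to 12 months, so a patient has up to 13 post-operative assessments.

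**The concern.** Item 1(b) fixes two choices.

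The first is conditioning. A time exists only where regaining is indicated, so the estimate describes successful recoveries. Question 2 allows for patients who never return and is put for everyone who has surgery. A patient deciding on an operation does not know which group they will fall into, so a figure for regainers alone answers a different question. The patients left out are the slow and failed recoveries that section 5.3 gives as the reason for enrolling higher-risk patients.

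The second is dating at the first single crossing. Both the baseline and each follow-up score carry measurement error, so one score at or above baseline can occur by chance in a patient with a lasting deficit.

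On the same scores both choices push one way. Patients without a regain time can only lengthen an all-patient quantile, and a first crossing cannot come later than a sustained one. The result is meant to inform consent.

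**Working it through.** **The plan's own figures.** The Protocol gives no expected time to regain, so there is no figure for 1(b) to reproduce. The 12% design rate is the lower end of the 8-19% range plus the 4% mortality: 8% + 4% = 12%. The sample size built on it reproduces: 1.96² × 0.75 × 0.25 / 0.03² = 800, and 800.3 / 0.12 = 6669, against the stated 6670. It has no bearing on this point.

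**Step 1: the relation without a model.** Let f be the share with no regain by month 12. The all-patient median is the 0.5/(1 − f) quantile of the regainers' times.

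| f | Source | Regainers' percentile equal to the all-patient median |
|---|---|---|
| 8% | section 5.1, lower end | 0.5/0.92 = 54th |
| 12% | section 5.1, design rate | 0.5/0.88 = 57th |
| 19% | section 5.1, upper end | 0.5/0.81 = 62nd |
| 23% | 19% + 4% deaths | 0.5/0.77 = 65th |

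The direction therefore holds whatever the shape of the recovery curve.

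**Step 2: size under a constant hazard (assumed).** Choose h so that a share f has not regained by month 12: h = −ln(f)/12. All-patient quantile: t(q) = −ln(1 − q)/h. Regainers-only quantile: t((1 − f)q).

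- f = 12%: h = 0.1767.
  - All patients: 0.693/0.1767 = 3.9 and 1.386/0.1767 = 7.8 months (median, 75th percentile).
  - Regainers: −ln(0.56)/0.1767 = 3.3 and −ln(0.34)/0.1767 = 6.1 months.
- f = 19%: h = 0.1384.
  - All patients: 5.0 and 10.0 months.
  - Regainers: −ln(0.595)/0.1384 = 3.8 and −ln(0.3925)/0.1384 = 6.8 months.
- f = 8%: h = 0.2105.
  - All patients: 3.3 and 6.6 months.
  - Regainers: −ln(0.54)/0.2105 = 2.9 and −ln(0.31)/0.2105 = 5.6 months.

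**Step 3: a second model.** Fix the regainers' median at 3 months, with a truncated exponential over 12 months (assumed). The all-patient median is then 3.4, 3.6, 4.1 and 4.4 months for f = 8, 12, 19 and 23%. The direction is the same and the size similar.

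**Step 4: chance crossings.** The Protocol gives no measurement error. Assume independent normal errors with SD 0.05-0.10 utility at baseline and at each of 12 monthly scores, and a constant true deficit. By simulation:

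| True deficit | At least one crossing | Two consecutive crossings | At or above baseline at month 12 |
|---|---|---|---|
| 0.10 | 37-71% | 11-37% | 8-24% |
| 0.20 | 2-37% | 0-11% | 0-8% |

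The range is too wide to give one size for this effect.

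**Step 5: what a two-score rule would do.** For a patient truly back at baseline throughout, the chance that all 12 scores fall below the measured baseline is 1/13, about 8%, because the baseline must be the largest of 13 exchangeable values. Simulation gives about 29% who never show two consecutive scores at or above baseline. A compulsory two-score rule would thus miss many true recoveries. The errors here are continuous; tied scores would soften both figures.

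**The case against.** The strongest reply is that the conditional reading rests on one word. No estimator or denominator is named, and a point estimate with an interval for a first occurrence could be a Kaplan-Meier or cumulative-incidence estimate. Censoring and competing death are commonly left to the statistical analysis plan, which is not shown. This limits how firmly the point can be put: it concerns the Protocol as worded. It does not remove the point, because an all-patient estimate would depart from the wording of 1(b), and that wording is what the Protocol fixes.

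A second reply is that the sizes rest on outside assumptions. A constant hazard is not in the Protocol, and section 6.1 expects most full recoveries within 3 to 6 months. That stands for the sizes but not for the direction (step 1). The chance-crossing figures depend on an unstated error SD and an assumed deficit, so it cannot be said in general that many patients with a lasting deficit will cross. Missed questionnaires can also delay an observed crossing and work the other way.

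A reader might infer that recovery will also look more common than it is. The documents do not support that. Item 1(b) reports a time, not a proportion, and section 5.1 frames the proportion not regaining at 12 months. Only if the second outcome were counted as ever having crossed would the proportion rise; on a month-12 reading, noise can lower it. Nor does the point reach the risk model: work packages 1(d), 2 and 3 use the third primary outcome, which sums gains and losses over follow-up.

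**Conclusion.** The point holds for time to recovery. As worded, 1(b) summarises first regaining in regainers only, so it would understate recovery time for the cohort and leave question 2 unanswered.

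Under a constant hazard the understatement at the median is about 0.6 months at 12% not regaining (3.9 against 3.3) and 1.3 at 19% (5.0 against 3.8, from unrounded values). At the 75th percentile it is 1.7 months (7.8 against 6.1) and 3.3 (10.0 against 6.8, from unrounded values). The effect is modest in the middle and larger among slow recoverers. Because assessments are monthly, a gap of 0.6 months may not show as a change in the observed median month.

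The first-crossing rule is a secondary matter of unknown size. It justifies a sensitivity analysis, not a new primary definition. This should be changed, but it affects one descriptive result and not the study's validity.

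**What to change.** Replace work package 1(b) with wording such as: the cumulative incidence of first regaining baseline QoL will be estimated from the date of surgery in all operated patients, with death as a competing event and censoring at the last questionnaire; the 12-month cumulative incidence and the times by which 50% and 75% of all patients have regained will be reported with confidence intervals.

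Add two items:

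- A sensitivity analysis with a sustained-regain definition, such as two consecutive scores at or above baseline, with a stated rule for a first crossing at month 12. It should not replace the main definition, because it misses true recoveries (step 5).
- The proportion at or above baseline at month 12, reported separately from the time summary, so that the second primary outcome has a fixed time point in line with section 5.1.

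The cost is a little more analysis work on questionnaires already scheduled, plus the dates of surgery and death. The reported recovery time will be less favourable. If 25% or more of patients have not regained by month 12, the 75% time would be reported as not reached.

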## 11. PATIENT & PUBLIC INVOLVEMENT

Patients and the public are represented by lay members of the Trial Steering Committee. Both the electronic and paper versions of data collection are currently being tested by our patient research ambassadors who will help refine the method to ensure it is user-friendly.

As a preliminary exploration, we approached a series of patients attending cardiac surgical clinics to consider surgery for their cardiac condition. They were shown the TUTE calculator (which predicts their likely benefit in terms of survival) and were asked if they would consider a similar tool predicting QoL outcomes useful to them. The response was invariably positive.

Throughout the course of the study we shall hold yearly patient events to discuss the construction of the QoL prediction tool and in particular the way patients would want this information presented to them so it will be understandable and of value. During the patient events we shall also ask previous cardiac patients what information they would have found useful in aiding them to make the decision to undergo surgery. This development will help design the end product that would be made available to patients and doctors.

Once data collection is completed, a descriptive report will outline the pattern of QoL loss and gain over time after cardiac surgery. The data will then be analysed by logistic regression to identify the factors predictive of loss and gain in QoL outcomes. A full analysis of factor interactions will be carried out. The data will be divided into a development dataset and a validation dataset. The development dataset will then be used to construct a number of risk models to predict the extent and likelihood of any QoL benefit or loss from cardiac surgery. All the models will then be tested for calibration and discrimination against the validation dataset to identify the most useful and robust model. The chosen model will then be developed into a QoL outcome calculator (QoLculator) which will be offered for testing and external validation, following which the calculator will be made available on-line and as a mobile phone app for patients and doctors.

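### Work package 1(c) plans the recovery curve as a descriptive average with no longitudinal model, so related non-response could bias the curve

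*Protocol*

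**What the plan says.** Protocol section 5.5 defines the first primary outcome as "a continuous variable of a difference in the single measure of QoL between the baseline stage and a follow-up stage". Work package 1 opens with "Perform descriptive statistics on (a) the first primary outcome at the stage immediately post-surgery", and the same list goes on to "c) the average trend of the first primary outcome over time". Section 11 describes the output in the same terms: "a descriptive report will outline the pattern of QoL loss and gain over time after cardiac surgery". A model is named only in work package 3: "Develop a risk model on the third primary outcome by logistic regression or multilevel logistic regression". That model, like the testing in work package 2, concerns the binary third outcome. The continuous outcome therefore appears only in descriptive items.

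On the data, section 2 says "QoL will be measured before the operation and monthly afterwards for 12 months", and section 6.1 adds an assessment at hospital discharge. Section 5.1 states "Anticipating a non-response rate of 20%, we will recruit an additional 1334 patients to compensate for this, giving a total of 8004", predicts 4% mortality in this higher-risk population, and has the steering committee monitor drop-out.

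The protocol does not say which patients enter the average at each month, how missing forms are handled in it, or how deaths are counted in it. Section 5.5 refers to a statistical analysis plan, which was not available for this review. That reference follows the proposal for a combined measure and most naturally concerns the choice of quality-of-life measure.

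**The concern.** The curve of early loss, return to baseline and later gain is the picture from which section 2 argues the whole study, and the second aim in section 3 asks for the net gain or loss. A plain average at each visit can rest on a different set of patients each month. It makes no use of what earlier forms show about patients who later stop answering. The outcome is a change from baseline, which removes differences in baseline level but not selection on the change itself.

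The protocol's own setting makes related loss plausible: higher-risk patients, monthly self-completed forms whose burden section 5.4 acknowledges, and a cited 8-19% whose quality of life falls and does not recover. If patients doing worse stop answering, the average rises although nobody has improved. If recovered patients stop answering, it falls. A large sample narrows the interval around the biased value and does not remove the bias.

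**Working it through.** **Inputs from the protocol.** Section 5.1 gives 6670 analysable patients, 8004 recruited, 20% non-response and 4% mortality. Section 6.1 gives discharge plus 12 monthly assessments: 1 + 12 = 13 post-operative differences per patient.

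**The plan's own figure.** The curve has no stated precision. The sample size on which it rests reproduces: 1.96² × 0.75 × 0.25 / 0.03² = 800.3, and 800.3 / 0.12 = 6669.2, against 6670 stated. With 20% of 8004 lost, 8004 × 0.80 = 6403 remain.

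**Assumptions not in the protocol.** These are the SD of the change, the strength of the link between earlier change and loss, and the reading of 20% non-response as cumulative loss by month 12.

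**Step 1: identity.** Let m be the share missing, O the mean of those observed and M the mean of those missing. The full mean is (1 − m)O + mM, so the bias of O is m(O − M). With deaths added to 20% of survivors, m = 0.04 + 0.96 × 0.20 = 0.232.

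| Assumed gap O − M | Bias, m = 0.20 | Bias, m = 0.232 |
|---|---|---|
| 0 | 0 | 0 |
| 0.05 | 0.010 | 0.012 |
| 0.10 | 0.020 | 0.023 |
| 0.15 | 0.030 | 0.035 |
| 0.20 | 0.040 | 0.046 |

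A negative gap gives the same sizes with the opposite sign.

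**Step 2: a flat course.** The simulation had 100,000 patients with 12 monthly changes. The true mean was −0.05 at every month, so there was no recovery. The between-patient SD was 0.15 and the within-patient SD 0.12 (total √(0.0225 + 0.0144) = 0.19). Patients who dropped out did not return. The log odds of loss depended on the previous month's change, and the intercept was tuned to the stated loss at month 12.

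| Loss by month 12 | Odds of loss per SD worse | Respondents' mean, months 1 / 6 / 12 | True mean, month 12 | Bias, month 12 | Sequential regression on earlier visits, month 12 |
|---|---|---|---|---|---|
| 20% | ×1 | −0.050 / −0.051 / −0.050 | −0.051 | 0.000 | −0.050 |
| 20% | ×e | −0.049 / −0.038 / −0.025 | −0.049 | 0.023 | −0.049 |
| 20% | ×e² | −0.050 / −0.029 / −0.013 | −0.050 | 0.037 | −0.050 |
| 23.2% | ×e | −0.050 / −0.036 / −0.022 | −0.050 | 0.027 | −0.049 |
| 23.2% | ×e² | −0.051 / −0.026 / −0.008 | −0.050 | 0.042 | −0.050 |

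Biases come from unrounded means. At 20% loss, about half (×e) or three quarters (×e²) of a true deficit of about 0.05 disappears.

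**Step 3: a milder setting.** This simulation had 200,000 patients, a true month-12 gain of 0.10, an SD of change of 0.19-0.23, 20% lost by month 12, and odds of loss 1.2 to 2.0 times higher per SD lower last score. The respondents' mean was too high by 0.006 to 0.027. The 95% half-width is 1.96 × SD / √6403, which is 0.0047 at SD 0.19 and 0.0056 at SD 0.23. The bias is thus about one to five half-widths. The curve would show a gain of about 0.106 to 0.127 instead of 0.10, so its sign does not change.

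**The case against.** The strongest reply is that this is analysis-plan detail. Estimator, covariance structure and missing-data handling are commonly left to the SAP, and an average trend could be a model-based mean curve. In part this stands: the protocol's wording does not rule out the proposed model. It does, however, class the curve as descriptive in two places and names a model where one is intended. That is a stated choice of method and can be questioned as such.

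A reader might infer three stronger things, which the documents do not support.

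- *That the protocol says the average is taken over whoever answered.* It names no analysis set. Use of available forms is the ordinary reading of a descriptive average, but it remains an inference.
- *That falling membership will be read as recovery.* This needs loss that accumulates and is concentrated in patients with worse change. Nothing in the protocol says who stops answering, and loss among recovered patients would bias the curve downwards.
- *That a mixed model removes the problem.* In the simulations loss depends on scores already observed, which is exactly what such a model corrects. The near-zero bias follows from that set-up and is no evidence about this cohort. Nor does the model settle deaths. Section 5.1 appears to count them as failures to regain quality of life (8% plus 4% gives its 12%), whereas an ordinary mixed model extrapolates scores for patients who have died.

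It is also fair that 1(c) is one of four descriptive items, and that work packages 2 and 3 do not depend on how it is averaged.

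**Conclusion.** The point holds in conditional form. Section 5.5 fixes the recovery curve as a descriptive average and names no longitudinal model, in a cohort with up to 13 post-operative differences per patient, 20% expected non-response and 4% expected mortality. If the average uses available forms and non-response is related to earlier change, the curve is biased and could show apparent recovery.

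The size is illustrative: about 0.006 to 0.04 utility at month 12, assuming 20-23% loss by then, SDs of change of 0.19-0.23, and odds of loss between 1.2-fold and e²-fold per SD worse. It is zero if loss is unrelated to change and reverses if patients doing better stop answering. The protocol supplies neither the SDs nor the dropout pattern, so direction and size stay open. The change is worth making before the data are seen, because it uses forms that are collected anyway. Confidence is medium.

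**What to change.** Replace item 1(c) in section 5.5, or state in the SAP and align 5.5 with it:

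> Mean change from baseline at discharge and months 1-12 among patients alive, from a linear mixed model for repeated measures (visit as a factor, baseline QoL, unstructured or equivalent covariance) using all available forms, with 95% CIs. Raw visit means, the number responding and the number dead are shown at each visit. Forms missing after death are not treated as ordinary missing data.

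Repeat this for the SF-12 measure. A standard fit does not by itself give a mean among patients alive, so the text should say how that is obtained. One way is to fill in from the model only the forms missing while the patient was alive, and to average over those alive at each visit.

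The cost is a few sentences and one standard model, with no new data. The downside is reliance on missing-at-random: loss that depends on unreported deterioration would still bias the curve. The raw means therefore stay as a supplement.

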### **3 RESEARCH QUESTION/AIM(S)**

- 1) who will experience QoL net improvement and who will not within 12 month of surgery
- 2) what is the net gain/loss of QoL that an operation may produce and for which patients
- 3) how long before a patient having a heart operation begins to benefit in terms of QoL

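### The sample size is set for predicting failure to regain baseline QoL, but section 5.5 models net benefit, and no suitable method is named for predicting amount or time

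*Protocol*

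**What the plan says.** Section 5.1 asks for a minimum of 6670 patients to produce "a predictor tool with a sensitivity of at least 0.75". It glosses this sensitivity as the "true positive rate to identify those patients that do not regain QoL after surgery", with a margin of ±0.03 "at the 95% confidence level". The rate used is given as follows: "a conservative estimate is that 12% of patients in this study would not regain QoL".

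Section 5.5 defines three primary outcomes on EQ-5D:

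- Outcome 1 is the continuous difference in QoL from baseline.
- Outcome 2 is whether baseline QoL has been regained (yes/no).
- Outcome 3 is whether the summed gains over follow-up exceed the summed losses (yes/no), that is, positive net benefit.

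Work package 1 is descriptive. It covers outcome 1 just after surgery and as an average trend, the time to first regaining baseline, and outcome 3. Work package 2 tests covariates against outcome 3. Work package 3 is: "Develop a risk model on the third primary outcome by logistic regression or multilevel logistic regression".

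Section 2 says that a risk model will predict three things. The first is who has net improvement. The second is "what is the net gain/loss of QoL that an operation may produce, and for which patients". The third, repeated as an aim in section 3, is "how long before a patient having a heart operation begins to benefit in terms of QoL". Section 2 also explains that "there will come a time when any QoL lost through surgery is 'paid back' by QoL gained", and that the patient truly starts to benefit from that point. Section 11 speaks of several risk models for the extent as well as the likelihood of benefit or loss, but names only logistic regression.

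**The concern.** The event behind the sample size is the complement of outcome 2, while the event to be modelled is based on outcome 3. The protocol defines them as separate outcomes. Section 2 also distinguishes patients who never regain the preoperative level from those whose later gain does not match the loss. A precision statement worked out for one event does not carry over to a model of another event with a different, unstated rate.

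The second part concerns the aims. A logistic model of a yes/no outcome gives a probability. It does not give how much QoL a patient gains or loses, nor when benefit starts. The only time analysis, work package 1(b), records first return to baseline, which is not the pay-back point that section 2 uses to define the start of benefit.

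At stake are a sample-size justification that does not belong to the tool being built, and two of the three promised predictions left without a method that could deliver them.

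**Working it through.** **Reproducing the stated figure.** Inputs from section 5.1: sensitivity 0.75, half-width 0.03, 95% confidence (z = 1.96), rate of not regaining QoL 0.12.

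- Cases needed = z² × Se × (1 − Se) / d² = 1.96² × 0.75 × 0.25 / 0.03² = about 800.3.
- Patients needed = 800.3 / 0.12 = about 6669, against 6670 stated.

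The figure reproduces, and it rests on failure to regain baseline at 12%.

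**Carrying it over to outcome 3.** A case is now a patient without positive net benefit. The protocol gives no rate p for this, so the rates below are assumptions. The half-width at N = 6670 is 1.96 × √(0.1875 / (6670 × p)), where 0.1875 = 0.75 × 0.25. The number needed for ±0.03 is 800.3 / p.

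| Assumed p | Cases in 6670 | Half-width | N for ±0.03 |
|---|---|---|---|
| 8% | 534 | 0.037 | 10004 |
| 12% | 800 | 0.030 | 6670 |
| 20% | 1334 | 0.023 | 4002 |
| 25% | 1668 | 0.021 | 3202 |

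The stated ±0.03 holds for the work package 3 model only if about 12% of patients lack net benefit.

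**Aims against analyses.**

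| Promised in section 2 | What section 5.5 provides | Gap |
|---|---|---|
| Who has net improvement | Work package 3, outcome 3 | None in the target; the sizing is for another event |
| Amount of gain or loss, and for which patients | Work package 1(a) and (c): change in the whole cohort | No method for the amount by patient |
| Time until benefit begins | Work package 1(b): first return to baseline | Different event; pay-back time is not an outcome |

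**Return to baseline against pay-back.** For a patient with an initial loss, the accumulated difference is still negative when QoL first returns to baseline, so in continuous time pay-back comes later. On monthly assessments it can fall at the same assessment but never earlier. An invented path shows the possible gap. QoL starts 0.30 below baseline, rises in a straight line to baseline at month 3, rises in a straight line to +0.10 at month 6, and stays there.

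- Loss area to month 3 = ½ × 3 × 0.30 = 0.45.
- Gain area, months 3 to 6 = ½ × 3 × 0.10 = 0.15, leaving 0.30 to recover.
- At 0.10 per month this takes 0.30 / 0.10 = 3 more months, so pay-back is at month 9 and return to baseline at month 3.

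The answer depends on how the difference is accumulated. Summing the monthly values alone gives −0.20 − 0.10 + 0 + 0.033 + 0.067 + 0.10 = −0.10 at month 6, and zero at month 7. Counting a discharge value of −0.30 as well moves it to month 10. Each is well after month 3, but the rule has to be stated.

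**The case against.** The strongest reply is that work package 3 models the right thing. Aim 1 in section 3 and the design statement in section 4.1 concern net improvement, which is outcome 3, and no aim requires a model of outcome 2. This stands. It places the fault in the sizing sentence of section 5.1 rather than in the choice of modelled outcome.

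A reader might infer that the tool the study is sized for will never be built. The documents do not support this. Section 11 plans several models, covers extent as well as likelihood, and speaks broadly of loss and gain in QoL outcomes. Section 5.5 also opens by saying that all six outcomes enter all the analyses. What can be said is that section 5.5 assigns no model to outcome 2.

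A reader might also infer that aims 2 and 3 have no analysis at all. That goes too far. Work package 1(a) and (c) describe the size of change in the cohort, and 1(b) gives a time, though to a different event. The protocol does not say that it will report time to regain as time to benefit; section 2 lists the two as separate questions.

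Finally, the form of a model for extent could be left to a statistical analysis plan. That is fair for the detail. It does not remove the disagreement between sections 2, 5.1, 5.5 and 11, which lies within the protocol. The deferral to a later plan in section 5.5 follows the discussion of which QoL measure to use, not the work packages.

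**Conclusion.** The point holds as a mismatch, not as a shown shortfall. The 6670 is correctly calculated for predicting failure to regain baseline at 12%, but the stated 0.75 ± 0.03 does not describe the model of net benefit. Over assumed rates of 8% to 25% the half-width runs from 0.037 to 0.021.

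It is tempting to treat 12% as a floor for the share without net benefit, and so to conclude that precision can only improve. That does not follow. Section 5.1 refers to QoL not regained after 12 months, and a patient above baseline for most of the year who falls below it by month 12 fails outcome 2 yet can have a positive net balance. The 12% also appears to combine 8% not regaining with 4% mortality, and the protocol does not say how a death counts on outcome 3. Nor do the documents support calling the study too small.

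On the aims, two things are missing: a method for the patient-level amount of gain or loss, and any outcome or analysis for pay-back time.

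**What to change.** - **Sizing.** Restate the sentence in section 5.1 for outcome 3, with an assumed rate of no net benefit and a range such as the one tabulated above. Alternatively, keep the sentence and add a model for outcome 2 to work package 3. The first option fits aim 1 and section 4.1 better.
- **Amount (aim 2).** Add a regression for the 12-month cumulative QoL difference from baseline, with centre as the grouping level if a mixed model is used.
- **Time (aim 3).** Define pay-back time as the first assessment at which the cumulative difference from baseline is at or above zero, and state how the difference is accumulated and whether the discharge value counts. Analyse it as time-to-event with death as a competing event. Keep work package 1(b), labelled as time to first return to baseline.
- **Consistency.** Align sections 2, 5.5 and 11 on which models are planned for which outcome.

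The cost is wording and extra analysis; the monthly QoL data are already planned in section 6.1 and Appendix 2. The competing-event analysis also needs dates of death after discharge. Sections 6.1 to 6.3 and Appendix 2 do not state that these are collected, so their availability must be confirmed first.
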